### **8.5.1 Exploratory Analyses**

Change in efficacy measures from pre-treatment to post-treatment to 3-month follow-up will be analyzed with descriptive statistics to represent trends in mean levels. Recognizing that the calculations will likely be underpowered, we will also perform ANOVAs of the secondary outcome measures. To assist in gauging the clinical relevance of these data relative to measurement error, and to overcome some of the limitations of the study's small sample size, Reliable Change Indices (RCI) will be calculated [181]. Data from efficacy measures will also be used to estimate effect sizes and intraclass correlation coefficients for use in larger, future studies.

Change in process measures (e.g., the HIM, QPIRS and GQ) over time will be analyzed with ANOVAs to assess the slopes of individual participants and of the whole sample.

Qualitative thematic analyses will be conducted according to the methods outlined in Section 6.3. Iterative inductive analyses will be performed with the aid of NVivo analytical software.

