#### 2.2.2 Exploratory Endpoints

Preliminary efficacy will be assessed with the primary clinical outcome measures:

- Change in demoralization will be defined as the difference in pre-treatment, post-treatment, and 3-month follow-up scores of the Demoralization Scale-II.
- Change in complicated grief will be defined by the difference in pre-treatment, post-treatment, and 3-month follow-up mean scores of the Inventory of Complicated Grief.

Preliminary efficacy will also be explored with the following secondary endpoints (See Section 5 for details on individual measures):

- Change in ART medication adherence will be defined as the difference in pre-treatment, post-treatment, and 3-month follow-up mean scores of the ART Medication Adherence Scale.
- Change in depression will be defined by the difference in pre-treatment, post-treatment, and 3-month follow-up mean scores of the Center for Epidemiologic Studies Depression Scale—Revised. Change in subject quality of life will be defined by the difference in pre-treatment, post-treatment, and 3-month follow-up mean scores of the McGill Quality of Life Questionnaire—Revised.
- Change in desire for hastened death will be defined as the difference in pre-treatment, post-treatment, and 3-month follow-up mean scores of Schedule of Attitudes towards Hastened Death.
- Change in anxiety will be defined as the difference in pre-treatment, post-treatment, and 3-month follow-up mean scores of the State-Trait Anxiety Inventory.
- Change in social support will be defined as the difference in pre-treatment, post-treatment, and 3-month follow-up mean scores of the Duke/UNC Functional Social Support Questionnaire-5.
- Post-traumatic growth due to the intervention will be defined by post-treatment and 3-month follow-up mean scores of Post-Traumatic Growth Inventory—Short Form.
- Change in PTSD symptoms will be defined as the difference in pre-treatment, post-treatment, and 3-month follow-up mean scores of the PTSD Checklist-5.
- Change in global clinical status will be defined as the difference in pre-treatment and post-treatment mean scores of the Clinical Global Impressions Scale completed by an clinical rater.
- Change in openness to experience will be defined as the difference in pre-treatment, post-treatment, and 3-month follow-up mean scores of the International Personality Item Pool—Openness to Experience-20 scale.

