#### 3.3.1 Inclusion Criteria

1. Gay-identified men  $\geq 50$  years old who are able to understand a written informed consent document and who are willing to sign it.
2. Laboratory confirmed HIV seropositive status; and diagnosed prior to 1996.
3. Moderate-to-severe demoralization, determined by a score of 8 or higher on the Demoralization Scale-II [27].

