### **3.6 Randomization Procedures**

Patients will not be randomized; this is an open-label pilot trial with one treatment arm.

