#### 6.4.1 Phone Screening

Potential subjects will be screened over the phone to assure that they understand the time requirements of the study, they identify as a gay man, they are at least 50 years old, they were diagnosed with HIV prior to 1996, they report experiencing moderate-to-severe symptoms of demoralization on the DS-II and that they report complicated grief on the ICG, and that they do not meet any major exclusion criteria (e.g., history of psychosis or bipolar disorder; recent active suicidal ideation). A brief orientation to the study protocol, including psychoeducation on psilocybin, will be provided to patients who are not excluded. The patient will then be scheduled for an in-person screening and enrollment visit.

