## 6.4.3 Baseline Assessments (Week 1)

### 6.4.3.1 Baseline Subject Assessments

Baseline assessments will be filled out during an individual therapy session wherein the subject will meet one or both of the group therapists in the week prior to the first group therapy session. Separately, the subject's caregiver/important other will be invited to meet with study staff for a brief interview on their relationship with the subject [see Appendix C for interview guides]. The individual session for the study subject is meant to build trust and rapport with the group therapists, to learn more about the subject's life history and struggles with his health, to elicit the subject's preferences and intentions for the treatment sessions, and to orient the subject further to the intervention protocol. If screening/enrollment measures were completed within 1 week of the baseline assessment, those measures will not need to be repeated.

- AMAS, AUDIT, CESD-R, CTC, DS-II, DUDIT, DUFSS-5, ECR-M16, ICG, IOS, IPIP-OE-20, MAIA-R, MQoL- RS, NR-6, PCL-5, PTGI-SF, SAHD, SCS-R, and STAI. A clinical rater will perform a CGI and C-SSRS(Interval) for each subject.

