## **8 Statistical Considerations and Evaluation of Results**

### **8.1 Study Design**

This open-label single-arm mixed-methods pilot study will use descriptive statistics and qualitative methods to evaluate safety and feasibility in terms of rates of adverse events, patient recruitment and retention, and feedback on the intervention's utility, content and duration. Given the small sample size of this study, small-to-medium effect sizes will likely be undetectable; and so descriptive statistics will be used to report changes in mean measures at baseline compared to the endpoint, and again at the 3-month follow-up. Exploratory ANOVAs will also be done to model changes in therapeutic process values (e.g., group cohesion) over time. Qualitative thematic analysis will also be used to evaluate verbal and written reports of patient and caregiver/important other experiences with the study in order to optimize implementation of the intervention in larger, future trials.

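### Section 8.5.1 makes no allowance for therapy group in the ANOVAs or in the precision of effect sizes meant for future trials; a smaller point is that the 1-week waiver lets a possibly qualifying DS-II score stand as baseline

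*Combined protocol and SAP*

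**What the plan says.** **Analysis.** The design has no control: "this is an open-label pilot trial with one treatment arm" (3.6). Section 8.1 states that "descriptive statistics will be used to report changes in mean measures at baseline compared to the endpoint", and again at 3 months. Section 8.5.1 adds: "Recognizing that the calculations will likely be underpowered, we will also perform ANOVAs of the secondary outcome measures". It also plans Reliable Change Indices, and then effect sizes and ICCs: "Data from efficacy measures will also be used to estimate effect sizes and intraclass correlation coefficients for use in larger, future studies". No factor is named for the efficacy ANOVAs. The process ANOVAs name the individual participant and the whole sample, but not the therapy group. No standard error, interval or group adjustment is stated for the effect sizes.

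**Clustering.** Sections 1.3 (Rationale for Group Therapy) and 8.2.1 both say that outcomes of members of the same group are likely to be interdependent. Section 8.2.1 uses this to explain why later trials must be large.

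**Baseline.** Section 2.2.2 lists DS-II and ICG as the primary clinical outcome measures and says: "Change in demoralization will be defined as the difference in pre-treatment, post-treatment, and 3-month follow-up scores of the Demoralization Scale-II". It does not say which visit supplies the pre-treatment value. Entry requires moderate-to-severe demoralization, "determined by a score of 8 or higher on the Demoralization Scale-II" (3.3.1). DS-II is taken by phone (6.4.1), at in-person enrollment (6.4.2) and at the Week 1 baseline (6.4.3.1). Section 6.4.3.1 then says: "If screening/enrollment measures were completed within 1 week of the baseline assessment, those measures will not need to be repeated". It makes no exception for DS-II.

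**The concern.** Two features affect the efficacy estimates that this pilot passes on (Abstract, Unique Aspects; 8.2.1; 8.5.1).

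1. **Precision (main).** If men in the same group change together, 18 men in 3 groups carry less information than 18 independent men. An interval or test that leaves group out is too tight. A later trial planned on such an estimate would take it as firmer than it is. Estimating an ICC beside the effect size does not repair this unless the ICC is used.

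2. **Baseline (minor).** A score that had to be 8 or more to admit a man is, on average, high by some measurement error. If it is also his pre-treatment value, part of the later fall is regression to the mean, and a single arm cannot separate that from improvement. The bias runs in the favorable direction.

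**Working it through.** **The plan's own figure.** Section 8.2.1 gives 18 enrolled, attrition up to 45%, and at least 8 completers. 8/0.55 = 14.5, so 15, which becomes 18 in whole groups of 6. 18 × 0.55 = 9.9 expected completers. The figure is coherent and not in dispute.

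**Inputs.** From the documents: groups of 6; 3 groups planned, 6 at most (1.4, 3.2); attrition up to 45%; 6 enrollments per 6 months (8.2.1); waitlist until 6 are available (6.4.2); cut-off 8; 7-day waiver. Assumed, because the documents give none: change-score ICC of 0.05, 0.10 or 0.20; screened DS-II mean 8 and SD 6; reliability 0.7 to 0.9; a 5% two-sided test.

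**Precision.** The design effect is 1 + (m − 1) × ICC. At m = 6 and ICC 0.10 it is 1 + 5 × 0.10 = 1.5, so the effective n is 18/1.5 = 12 and the standard error is understated by √1.5 = 1.22.

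Approximate error of a t test that ignores group, SD of change = 1:
- true SE = √(1.5/18) = 0.289
- expected sample variance = (18 − 1.5)/17 = 0.971, so naive SE = √(0.971/18) = 0.232
- ratio 1.243; 2.110/1.243 = 1.697; two-sided tail of t with 17 df = 0.108

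Simulation agrees (3 groups of 6):

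| ICC | SE multiplier, m = 6 | True error, full groups | True error, 45% random dropout |
|---|---|---|---|
| 0.05 | 1.12 | about 8% | about 6% |
| 0.10 | 1.22 | about 11% | about 8% |
| 0.20 | 1.41 | about 17% | about 11% |

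Six full groups give nearly the same errors, so reaching 36 patients does not remove the problem.

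**What the ICC estimate can bear.** An observed ICC of 0.10 has a 95% interval of about −0.12 to 0.92 from 3 groups of 6, and −0.08 to 0.61 from 6 groups. Section 1.3 (Rationale for Dosing Regimen) allows the first group's dose to differ from later groups'. If that shifts the first group's mean change by an assumed d SD, the between-group variance rises by d²/3 with 3 groups. A true ICC of 0.10 then reads as (0.10 + 0.03)/1.03 = 0.13 at d = 0.3, and (0.10 + 0.083)/1.083 = 0.17 at d = 0.5.

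**Baseline, per carried-over patient.** Expected spurious fall = (1 − r) × SD × φ(z)/(1 − Φ(z)), with z = (7.5 − 8)/6 = −0.083. This is (1 − r) × 6 × 0.3976/0.5332 = (1 − r) × 4.47:
- enrollment score alone qualifies: 1.34, 0.89, 0.45 points at r = 0.7, 0.8, 0.9
- phone and enrollment must both be 8 or more: 0.90, 0.56, 0.26 (simulation)
- only the phone score qualifies: about 0

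**Share carried over.** Mean spacing of enrollments is 182/6 = 30.3 days. If baseline follows the sixth enrollment at once, the sixth man is always in the window and 7/30.3 = 0.23 others are on average: 1.23/6 = 20.5%. At 6.9 days it is 16.7%. Beyond 7 days it is 0.

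**Cohort mean.** At most 0.205 × 1.34 = 0.27 points; at least 0. At an assumed 3 enrollments a month the ceiling is 0.282 × 1.34 = 0.38.

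**The case against.** **On precision.** Section 8.5.1 names no ANOVA factors at all, so its silence on group is not a decision to ignore it. The plan calls these analyses exploratory and probably underpowered, leans on description, and commits to an ICC. All of that is true and limits the weight of the point. It does not close the gap: the effect sizes are explicitly for reuse, and nothing in 8.5.1 says how their uncertainty allows for an interdependence that the plan itself predicts.

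A reader might infer that the DS-II and ICG results will be tested at up to 17% error. The documents do not support that. Section 8.5.1 names ANOVAs for the secondary outcomes, while 2.2.2 treats DS-II and ICG as the primary clinical measures; no test, alpha or interval is stated for them. The error figures describe a 5% test among the secondary ANOVAs, if one is done without group.

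**On baseline.** The bias is small. The 0.27-point ceiling needs the lowest reliability, entry decided by the enrollment score alone, and baseline held as soon as the sixth man enrolls. A reader might infer that regression to the mean through the waiver explains much of any DS-II improvement. The waitlist rules that out on these figures. Nor do the documents say that the enrollment score decides entry: 3.3 links baseline evaluations and eligibility without naming a reading, 3.3.1 names none, and the phone screen requires that "they report experiencing moderate-to-severe symptoms of demoralization on the DS-II and that they report complicated grief on the ICG". For ICG the concern is weaker still, since ICG appears as a screen only by phone. Further DS-II readings during and after treatment also make the trend less dependent on one value.

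A fresh reading is only a partial cure. If symptoms also drift slowly (assumed 50% trait, 35% state, 15% noise, correlation time 8 to 16 weeks), it removes about 0.5 to 0.8 of 1.2 to 1.7 points per carried-over patient.

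**Conclusion.** The point holds as a low-cost improvement to the exploratory efficacy analyses. The primary safety and feasibility analysis is untouched, and no confirmatory conclusion depends on it.

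The precision gap is the main part. Its size rests entirely on an assumed ICC, and dropout lessens it. The baseline part is minor: it is nil if only the phone score decides entry or if baseline falls more than 7 days after the sixth enrollment. Confidence is medium, because the ICC, the DS-II reliability and the deciding DS-II reading are not given in the documents.

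**What to change.** **8.5.1.** Report each effect size, and any interval or test of change, with the patient-level interval multiplied by √(1 + (m − 1) × ICC) at several stated ICC values, for example 0, 0.05, 0.10 and 0.20. Take m as the sum of squared observed group sizes divided by patients observed. Use this one method for any number of groups, with a group-level interval only as an optional sensitivity analysis. Switching method by number of groups would mislead: at ICC 0.10 the half-width is 0.59 SD of change for 3 full groups with the multiplier, but 0.71 for 4 at group level, against 0.50 if the multiplier is kept. Report the ICC with its interval, and state that it is very imprecise and may mix dose with clustering.

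**6.4.3.1 and 2.2.2.** Exempt DS-II and ICG from the 1-week waiver, do not use the Week 1 reading for eligibility, and define the pre-treatment value of these two measures as that reading. State that this reduces selection effects in a single-arm study but does not remove them.

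**Cost.** Wording in three sections, and at most 35 repeated items (16 DS-II, 19 ICG) for about 4 of 18 patients (18 × 0.205 = 3.7). Intervals widen: at ICC 0.10 the median half-width goes from about 0.48 to 0.59 SD of change with 3 full groups, and from 0.66 to 0.74 with 45% dropout. The multiplier depends on the ICC stated. If the true ICC is 0.20 and 0.05 or 0.10 is used, the error with 3 full groups is still 12.5% or 9.6%, which is why several values must be shown.

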#### *Rationale for Dosing Regimen*

Griffiths et al [138] have characterized the dose-response relationship of oral psilocybin in healthy volunteers. They found that when considering the odds of attaining a complete mystical experience versus having a temporary anxiety reaction during the drug experience (lasting on the order of minutes), the optimal dose likely falls between 0.29mg/kg and 0.43mg/kg [138]. This dose range has been successfully used in studies of psilocybin-assisted psychotherapy for existential distress in cancer patients [19, 20], severe alcohol use disorder [107] and tobacco use disorder [108]. The current study will employ a dose of 0.3mg/kg po in the first group, and if this is well tolerated will then escalate to 0.36mg/kg po in subsequent groups.

The dosing of the psychotherapy—8 weekly sessions—was chosen on the basis of comparison with similar group psychotherapies for existential distress in palliative care patients. The group psychotherapy with the best evidence-base for treating existential distress in palliative care patients, Meaning-Centered Group Psychotherapy, also employs 8 sessions [139]. The group psychotherapy with the best evidence-based for treating complicated grief has 16 weekly sessions [140]. Our protocol uses a modified course of Brief Supportive-Expressive Group Therapy, which was designed and tested as a 12-week course of treatment [76]. Empirical data suggest that group therapies lasting at least 12 sessions are shown to have greater correlations between group cohesion and clinical outcomes [129]. We hypothesize that psilocybin will catalyze group cohesion in a shorter period of time, thus making 12-16 weeks of group therapy unnecessary for detecting comparable results with regards to cohesion and clinical outcomes.

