### Secondary

1. The difference in pre- and post-treatment mean scores of demoralization, complicated grief, depression, PTSD, shame, anxiety, quality of life, functional social support, post-traumatic growth, openness to experience, attachment security, mindfulness, global clinical impressions and ART medication adherence will trend toward significant improvement. These improvements will be sustained at 3-month follow-up.
2. The difference in pre- and post-psilocybin rates of change of group cohesion and group process will trend toward significant improvement.
3. Qualitative analyses of subject behavior and caregiver/important other reports will lead to greater understanding of the interpersonal mechanisms of action of psilocybin-assisted psychotherapy.

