- Change in mindfulness will be defined as the difference in pre-treatment, post-treatment, and 3-month follow-up mean scores of subscales of the Multidimensional Assessment of Interoceptive Awareness.
- Change in social connectedness will be defined by the difference in pre-treatment, post-treatment, and 3-month follow-up mean scores of the Social Connectedness Scale—Revised.
- Change in Nature Relatedness will be defined by the difference in pre-treatment, post-treatment, and 3-month follow-up mean scores of the Nature Relatedness Scale, Short Form Version.
- Change in alcohol and drug use will be defined by different in the baseline and 3-month follow-up AUDIT and DUDIT scores

Psychotherapeutic process and mechanisms will be explored with the following endpoints:

- Change in group cohesion will be defined as the difference in rate of Group Questionnaire score change pre- and post-psylocybin.
- Change in group process will be assessed as the difference in rate of progression of

---

the Hill Interaction Matrix score pre- and post-psilocybin.

- Change in group process will be assessed as the change in the Individual Group Member Interpersonal Process Scale over time.
- Expectancy effects will be estimated based on the pre-psilocybin total score of the Credibility/Expectancy Questionnaire.
- Subjective experience of a psilocybin treatment session will be evaluated with the Mystical Experience Questionnaire—30 and the Challenging Experience Questionnaire.
- Change in attachment security will be defined as the difference in pre-treatment, post-treatment, and 3-month follow-up mean scores of the Experiences in Close Relationships scale—Modified 16.
- Qualitative analysis of therapy session video footage, semi-structured patient interviews, focus groups and process notes written by study staff.
- Change in inclusion of other in self will be defined by the difference in pre-treatment, post-treatment, and 3-month follow-up results of the Inclusion of Other in Self measure.

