## 6.4.4 Treatment Period

### 6.4.4.1 Group Therapy Sessions #1-4 (Weeks 2-3)

Patients will undergo four 90-minute group therapy preparatory sessions (2 per week) that will be audio and video recorded. Video footage of a random sampling of sessions will be analyzed with the HIM, SEGT-TG and the GPIRS. Patients will fill out the GQ after the sessions in Week 2 and 4. A clinical rater will administer the C- SSRS(Interval) to each subject at each weekly study visit.

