### **6.4.4.3 Group Therapy Sessions #5-10 (Weeks 6-8)**

Patients will undergo six group therapy sessions each 90-minutes long. Video footage of a random sampling of sessions will be analyzed with the HIM, SEGT-TG, IGMIPS and the GPIRS. Prior to each session, patients will be screened for adverse events and evaluated with the CSSR-S. Prior to sessions 5, 7 and 9, participants will fill out the CTC. After sessions 6, 8 and 10, participants will fill out the GQ. At the end of session 5, participants will fill out these questionnaires: CESD-R, DS-II, ICG, PCL-5, HARSI. After sessions 7 and 10, participants will fill out the DS-II and ICG.

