### **8.2 Determination of Sample Size and Accrual Rate**

#### **8.2.1 Sample Size and Power Estimate**

This pilot study of the safety and feasibility of psilocybin-assisted group therapy aims to enroll at least 18 subjects, and will have a maximum total sample size of 36. We estimate needing to enroll 18 subjects given attrition rates of up to 45% reported in trials of other group therapies for existential distress in palliative care patients [114]. For comparison, four different safety and feasibility pilot studies of psilocybin-assisted psychotherapy have been conducted over the last two decades, and have included 9, 10, 12 and 15 patients each [18, 107, 108, 110]. Four recently published feasibility pilot studies of meaning-focused group psychotherapies for palliative care patients have included 5, 11, 11, and 16 patients each [40, 178-180].

Group therapy studies should include at least 2 groups of at least 4-6 members [135], so we plan to have at least 8 subjects complete the intervention. We expect to be able to enroll at least 6 subjects every 6 months.

Because the proposed study is a pilot focused on investigating safety and feasibility, power calculations for efficacy measures are not indicated. Pilot studies are often used to estimate values that are then utilized in power calculations for full-scale trials. Indeed, we will estimate effect size (ES) and the intraclass correlation coefficient (ICC) [132] for the intervention based on our preliminary efficacy results. Group psychotherapy trials generally require large sample sizes to demonstrate statistical significance in change in efficacy measures given the likely interdependence of clinical outcomes when interventions are delivered in groups [132, 133]. Thus, future full-scale trials can utilize our estimates to derive adequate, and likely large, sample sizes.

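### The cohesion and group-process hypothesis is a before/after-psilocybin difference in rate of change, but the planned ANOVAs over time name no term that estimates it

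*Combined protocol and SAP*

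**What the plan says.** Section 1.4, secondary hypothesis 2: "The difference in pre- and post-psilocybin rates of change of group cohesion and group process will trend toward significant improvement".

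Section 2.2.2 carries this into the endpoints. For the GQ: "Change in group cohesion will be defined as the difference in rate of Group Questionnaire score change pre- and post-psylocybin". The HIM endpoint is defined the same way, as a pre/post difference in rate of progression.

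The analysis is described in two places. Section 8.1: "Exploratory ANOVAs will also be done to model changes in therapeutic process values (e.g., group cohesion) over time". Section 8.5.1: "Change in process measures (e.g., the HIM, QPIRS and GQ) over time will be analyzed with ANOVAs to assess the slopes of individual participants", the sentence then adding the whole sample. Neither passage mentions a before/after-psilocybin factor, its interaction with session, or a difference between two slopes.

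GQ timing before the drug session (Section 6.4.4.1): "Patients will fill out the GQ after the sessions in Week 2 and 4". After it (Section 6.4.4.3): "After sessions 6, 8 and 10, participants will fill out the GQ". The HIM is rated on video of a random sample of sessions. Section 8.4.1 puts everyone who attended at least one group session into the process analyses. Section 3.6 confirms a single arm.

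**The concern.** A difference between two rates and a change over time are separate questions. A time ANOVA takes equal session means as its null; a whole-course slope takes zero trend. Either null can be false while the rate is identical before and after psilocybin.

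The protocol itself suggests that this is a realistic case. The dosing rationale in Section 1.3 says "We hypothesize that psilocybin will catalyze group cohesion in a shorter period of time", which is a claim of acceleration and implies that cohesion would also build without the drug, only more slowly. A rising GQ is then what ordinary group therapy would produce.

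There is no control arm, so the within-person comparison of phases is the only quantitative evidence on whether psilocybin altered the course of cohesion. If the report gave a time effect in its place, growing familiarity within the group could be credited to the drug.

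**Working it through.** **Is there a plan figure to reproduce?** No. The documents state no alpha, power, GQ SD or expected growth for the process analyses. Everything below rests on assumptions, so ranges are shown.

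**Inputs from the documents.** GQ after sessions 6, 8 and 10 (Section 6.4.4.3). For the pre-drug readings I take sessions 2 and 4, as the assessment timetable appears to show; Section 6.4.4.1 says Weeks 2 and 4 although its heading places sessions 1–4 in Weeks 2–3. Sample size: the study "aims to enroll at least 18 subjects, and will have a maximum total sample size of 36". With the 45% attrition cited in Section 8.2.1, 18 × 0.55 = 9.9, so n = 10 is also shown.

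**Set A, assumed.** Between-person SD 1 (the unit), residual SD 0.7 (variance 0.49), two-sided 5%, the same linear slope b per session before and after, no clustering by therapy group. The sum of squared deviations of sessions 2, 4, 6, 8, 10 about their mean is 16 + 4 + 0 + 4 + 16 = 40.

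- Time ANOVA: noncentrality = n × b² × 40 / 0.49. At n = 18, b = 0.10: 18 × 0.01 × 40 / 0.49 = 14.7 on 4 and 68 df.
- Whole-course slope: noncentrality = b√n / √(0.49/40). At n = 18, b = 0.10: 0.10 × 4.243 / 0.1107 = 3.83.
- Phase contrast: (GQ10 − GQ6)/4 − (GQ4 − GQ2)/2, whose expectation is zero for any steady b.

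Rejection with no psilocybin effect (20,000 simulated trials per cell; the noncentral F and t distributions agree):

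| Growth b per session | Time ANOVA, n = 18 | Time ANOVA, n = 10 | Whole-course slope, n = 18 | Phase contrast |
|---|---|---|---|---|
| 0.05 | 28% | 16% | 44% | about 5% |
| 0.10 | 86% | 55% | 95% | about 5% |
| 0.15 | 100% | 92% | 100% | about 5% |

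**Set B, assumed.** Within-person SD 1, between-person SD 1, person-slope SD 0.1 per week, readings in weeks 2, 3 | 6, 7, 8, n = 18 (2,000 trials per cell):

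| Total steady rise, first to last reading (within-person SDs) | Time ANOVA | Whole-sample slope | Phase contrast |
|---|---|---|---|
| 0.25 | 9% | 12% | 5% |
| 0.5 | 25% | 34% | 6% |
| 0.75 | 50% | 63% | 5% |
| 1.0 | 76% | 84% | 5% |
| 1.5 | 98% | 99.5% | 5% |

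Adding group-level slope variation (SD 0.1) with zero mean growth already takes the ANOVA to 12% and the slope test to 15%; the contrast stays at 5%.

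**Precision of the contrast (Set A).** Per-person SD = √[(0.25 + 0.25 + 0.0625 + 0.0625) × 0.49] = √0.306 = 0.553. The 95% half-width is 2.110 × 0.553/√18 = 0.28 SD per session at n = 18 and 2.262 × 0.553/√10 = 0.40 at n = 10. For a true slope change of 0.2 SD per session, power is about 30% and 18%.

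**Sensitivity to a curved natural course (Set A).** Suppose no psilocybin effect and decelerating GQ means of 0, 0.60, 0.92, 1.10, 1.20. The pre-drug slope is 0.60/2 = 0.30, the post-drug slope (1.20 − 0.92)/4 = 0.07, and the difference −0.23. The contrast then rejects in about 38% of trials at n = 18 and 21% at n = 10, nearly always towards a falling slope.

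**The case against.** A reader might infer that the plan has committed itself to the wrong test and that this test is likely to declare a psilocybin effect where there is none. The documents do not support that. No passage says that an omnibus time effect will decide hypothesis 2. Section 8.5.1 speaks of slopes, and read beside Section 2.2.2 these could be meant as phase-specific slopes. The sentence also covers several process measures, some without a pre/post-rate endpoint: the Individual Group Member Interpersonal Process Scale endpoint is simply change over time. 'Likely' would need a growth rate and SD that appear nowhere, and for slow growth the rejection rate at n = 18 is 9–28%.

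The stakes are also limited. These analyses are exploratory, the hypothesis predicts only a trend, a biostatistician oversees or reviews interpretation, and the primary safety and feasibility conclusions do not depend on them.

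The contrast has weaknesses of its own. Its 5% error rate holds only if natural growth is roughly linear, its power is low, and a man-by-man calculation would drop anyone missing either pre-drug GQ reading.

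All of this stands. It limits the point to under-specification and shapes the remedy. It does not make a time effect, or a single whole-sample slope, an estimate of a difference between two rates.

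**Conclusion.** The hypothesis and both endpoints are a difference in rate of change across psilocybin, and the analysis text names nothing that estimates it. This follows from the text alone.

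The size is conditional. If the time ANOVA is used for hypothesis 2 at n = 18, steady growth alone gives rejection of about 9–28% when growth is slow (a total rise of roughly 0.25 to 0.6 within-person SD) and over 75% when it is faster (about 1 SD or more), against a nominal 5%. These figures rest on assumed SDs, linear growth and a two-sided 5% level. They show what could happen under one reading of the plan and do not forecast the trial's result. The gap is worth closing before the process data are analysed.

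**What to change.** In Sections 8.1 and 8.5.1, for the GQ and the HIM, name the phase-by-session term (post-psilocybin slope minus pre-psilocybin slope) as the analysis of hypothesis 2.

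- **GQ:** a mixed model with session, phase and phase-by-session, and random effects for participant and, where estimable, therapy group. Men with incomplete readings then stay in, in line with Section 8.4.1.
- **HIM:** the same contrast applied to the rated sessions. A slope in each phase needs at least two rated sessions there, so the random sampling should allow for this.
- **Reporting:** give the estimate with its 95% CI, label it exploratory, and state that a time effect alone is not evidence of a psilocybin effect.
- **Timing:** reconcile the pre-drug GQ occasions in Section 6.4.4.1 with its heading and the assessment timetable.

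The cost is a few sentences and no extra GQ readings or visits. Two downsides should be stated in the plan. The pre-drug GQ slope rests on two readings, so the interval is wide (about ±0.28 SD per session at n = 18 and ±0.40 at n = 10 under the assumed SDs). And in a single arm a non-linear natural course of cohesion remains confounded with psilocybin, so even this contrast cannot isolate a drug effect.
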